## 1.0 BACKGROUND AND HYPOTHESES

### 1.1 Background:

Postoperative constipation is among the most common complaints among women after gynecologic surgery. In the early postoperative period a temporary delay in gastrointestinal motility can be expected secondary to manual manipulation of bowel and medications including anesthesia and opiates. Postoperative constipation is a significant problem as return of bowel function is the most common reason for delayed hospital discharge after abdominal surgery. Without intervention, the average time to bowel movement after benign gynecologic and urogynecologic surgery is 4 days +/- 1.5 days. Delayed time to first bowel movement after surgery is often associated with patient discomfort and contributes to a delay in postoperative recovery.

The exact pathophysiology of delayed return of bowel function is unknown. Bayliss and Starling described the presence of inhibitory spinal reflexes acting on the bowel in 1899, which were later identified to be sympathetic inhibitory pathways in the autonomic nervous system. Sympathetic inhibition involves prevention of acetylcholine release from excitatory fibers in the myenteric plexus. The enteric nervous system has also been implicated as Holzer and Lippe suggested the role of Substance P, a neurotransmitter associated with pain. Bult et al. proposed that nitric oxide is the major inhibitory nonadrenergic noncholinergic neurotransmitter in the enteric nervous system. Hormones and neuropeptides such as vasoactive intestinal peptides, inflammation mediated by macrophages and neutrophils, general anesthesia and opioid narcotics may also contribute to the pathophysiology of delayed return to bowel function after surgery.

### 1.2 Previous Studies:

The standard at our institution for post-operative bowel regimen is the use of docusate sodium twice daily. Docusate lowers the surface tension of stool, facilitating the passage of water into the stool. There have been two studies looking at post-operative bowel regimens after anorectal and pelvic reconstruction surgeries which demonstrated a reduction in time to first bowel movement with the use of docusate sodium plus an additional therapy (senna or polyethylene glycol 3350, fiber wafers and bisacodyl suppositories) compared to docusate sodium alone.

Prunes (dried plums, *Prunus domestica*) has been studied for treating constipation among those with chronic constipation. The exact mechanism by which prunes relieve constipation is not fully understood, but its efficacy is attributed to the high fiber content and the presence of chlorogenic and neochlorogenic acids which pass undigested into the colon. Prunes can be a safe and inexpensive addition to the bowel regimen of women undergoing benign gynecologic surgery. However, no study has yet evaluated the efficacy of adding prunes to the bowel regimen after gynecologic surgery. We hypothesize that prunes will enhance the return of intestinal function as measured by time to first bowel movement.

### 1.3 Significance

Better management of constipation and its associated discomfort addresses a major postoperative complaint among patients, and has the potential for significant savings for healthcare systems. Postoperative constipation is associated with longer hospital stays and contributes, in part, to the \$1 billion spent annually in the United States on treatment of postoperative nausea, vomiting and constipation. With an increased awareness of cost-conscious healthcare delivery, postoperative constipation management is an opportunity to reduce costs through an initiative that directly improves patient care.

## 2.0 OBJECTIVES AND PURPOSE

2.1 To determine the time to first bowel movement after benign gynecological surgery in women treated with prunes and docusate compared to those treated with docusate alone.

2.2 To determine pain associated with first bowel movement (scale 1-10), stool consistency using Bristol stool form scale, the need for additional laxatives, compliance and patient satisfaction.

## 3.0 STUDY DESIGN

3.1 This is a prospective, randomized control trial.

3.2 Identification of Subjects:

All potential participants will be identified in the Gynecology or UroGynecology clinic at Los Angeles County-University of Southern California (LAC+USC) Medical Center. On average, between 8-10 patients undergo benign gynecologic surgery with overnight stay per week.

3.3 Recruitment of Participants:

Each eligible participant will be approached in person by one of the study investigators and invited to participate in the study. The informed consent will be reviewed in detail with a physician and the potential participant will be given time to ask questions. The potential participant will be allowed to take a copy of the consent home to review and discuss with family or friends.

3.4 Evaluation Pre-Intervention:

Clinical information will be collected.

3.5 Intervention:

1. Participants that undergo benign gynecologic surgery without intraoperative complications that are admitted overnight will be randomized to one of two groups.

2. Participants in the treatment arm will receive a 12 oz package of prunes on the morning of postoperative day 1.

3. All participants will receive the standard 100 g docusate sodium twice daily. Participants in the treatment arm will be instructed to consume 4 oz prunes (12 prunes) daily.

4. Additional laxatives will not be routinely given. There will be additional laxative medications (Milk of Magnesia) available for participants as needed, and it will be recorded that additional laxatives were needed.

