## 6.0 STRATIFICATION/DESCRIPTIVE FACTORS/RANDOMIZATION SCHEME

6.1 Stratification factors. N/A

6.2 Descriptive factors. Age, height, weight, self-described race and ethnicity, menopausal status, baseline frequency of bowel movements, laxative use, fiber use, medications used, and baseline stool consistency.

6.3 Randomization plan:

On morning of post-operative day 1, participants who do not meet exclusion criteria will be randomized to the treatment or control group at a 1:1 ratio. Randomization blocks of 6 will be applied in this study to ensure balanced treatment assignments throughout the recruitment period. The randomization assignment list will be generated by the study statisticians. [name]. Ph.D

Participants will be standardly administered 100 g of docusate twice daily for three days per existing routine post-operative care. In addition, we will administer a total of 12 oz of prunes to the study group which are pitted and preservative free. The prunes will be provided to the participant in a sealed package. The study group be instructed to eat 4 oz of prunes daily. The control group will be advised to avoid prune products for 3 days. Each group will be given a diary to note their prune and/or docusate consumption and details of their first bowel movement.

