### If Yes to any of the above, do not randomize.

Was preoperative bowel prep administered?                      Yes                      No

Primary indication for surgery

- Adnexal mass
- Abnormal uterine bleeding (with or without fibroids)
- Fibroid uterus (without abnormal uterine bleeding)
- Pelvic organ prolapse
- Other (Please indicate) \_\_\_\_\_

Procedures performed

- Open abdominal hysterectomy
- Open sacral colpopexy
- Open surgery, other
- Vaginal hysterectomy
- Other vaginal only surgery
- Laparoscopic or robotic hysterectomy (including laparoscopic or robotic assisted vaginal hysterectomy)
- Laparoscopic or robotic sacral colpopexy
- Laparoscopic or robotic surgery, other
- Posterior colporrhaphy
- Burch urethropexy alone
- Other (Please indicate) \_\_\_\_\_

Estimated blood loss \_\_\_\_\_ ml

Surgery start time \_\_\_\_\_

Surgery end time \_\_\_\_\_

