**Prunes Data Collection Sheet**  
**Data collected on post op day 3**

Day of discharge to home (if discharged)  
Time of discharge to home (if discharged)

1

2

3

---

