# Prunes Data Collection Sheet

## Self administered survey

Have you had a bowel movement since surgery? Yes No

If Yes, When did you have your first bowel movement?

Date \_\_\_\_\_ Time \_\_\_\_\_

How *painful* was your first bowel movement?

Not at all painful 0    1    2    3    4    5    6    7    8    9    10 Very painful

Which picture best describes your bowel movement (Circle one number)?

1    2    3    4    5    6    7

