### Bristol stool chart

Type 1		Separate hard lumps, like nuts (hard to pass)
Type 2		Sausage-shaped but lumpy
Type 3		Like a sausage but with cracks on its surface
Type 4		Like a sausage or snake, smooth and soft
Type 5		Soft blobs with clear-cut edges (passed easily)
Type 6		Fluffy pieces with ragged edges, a mushy stool
Type 7		Watery, no solid pieces, Entirely liquid

How satisfied were you with the treatments you received to help you with bowel movements after the surgery?

Not at all satisfied 0    1    2    3    4    5    6    7    8    9    10 Extremely satisfied

How satisfied were you with your surgery overall?

Not at all satisfied 0    1    2    3    4    5    6    7    8    9    10 Extremely satisfied

How many docusate did you take on day 1? \_\_\_\_\_

How many docusate did you take on day 2? \_\_\_\_\_

How many docusate did you take on day 3? \_\_\_\_\_

Did you use any laxatives? Yes No

If yes, what? \_\_\_\_\_

If yes, what day? \_\_\_\_\_

If in study group (prunes):

How many prunes did you eat on day 1? \_\_\_\_\_

How many prunes did you eat on day 2? \_\_\_\_\_

How many prunes did you eat on day 3? \_\_\_\_\_

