## Appendix IV: Prune Diary

Mark on the chart below what time you ate a prune.

Marque en la tabla debajo de qué hora usted comió una ciruela pasa.

	Day 1	Day 2	Day 3
6am			
7am			
8am			
9am			
10am			
11am			
12noon			
1pm			
2pm			
3pm			
4pm			
5pm			
6pm			
7pm			
8pm			
9pm			
10pm			
11pm			
12midnight			
1am			
2am			
3am			
4am			
5am			

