**Appendix V: Stool softener diary**

Mark on the chart below what time you took your stool softener medication.

Marque en la tabla debajo de qué hora tomó su medicación suavizante de heces.

	Day 1	Day 2	Day 3	Day 4	Day 5
6am					
7am					
8am					
9am					
10am					
11am					
12noon					
1pm					
2pm					
3pm					
4pm					
5pm					
6pm					
7pm					
8pm					
9pm					
10pm					
11pm					
12midnight					
1am					
2am					
3am					
4am					
5am

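### The rescue laxative is recorded by day only, so when a dose and the first bowel movement fall on the same day the forms cannot show which came first

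*Combined protocol and SAP*

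**What the plan says.** Section 3.5, item 4, makes a rescue laxative available to both arms: "There will be additional laxative medications (Milk of Magnesia) available for participants as needed, and it will be recorded that additional laxatives were needed". It gives no trigger, no earliest hour, and no plan to note when a dose was taken.

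The self-administered survey in Appendix III asks whether any laxative was used, which one, and "If yes, what day". The Spanish version likewise asks only for the day. For the outcome, the same survey asks "If Yes, When did you have your first bowel movement" and provides a date and a time.

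Section 10.0 defines the primary endpoint as time to first bowel movement in hours and treats laxative need as a yes/no secondary endpoint compared by chi-square. It includes all eligible patients who begin treatment. Section 13.0 compares the primary outcome by two-sample t-test, with no separate rule for movements that follow a laxative.

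**The concern.** Rescue acts directly on the primary outcome. A woman who takes Milk of Magnesia while waiting may have her first movement because of it, so a reader will ask two things of each arm: how many first movements followed a laxative, and how long after surgery the first dose was taken. With the day alone, the first answer is a range and the second is known only to within a day for each woman.

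The question is a natural one here because participants know their arm. One arm is given prunes, and for the other "The control group will be advised to avoid prune products for 3 days". The only masking stated is that of the telephone caller (section 3.6). A time that was never asked for cannot be supplied afterwards for a dose taken at home.

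**Working it through.** **1. The plan's own figure.** Section 13.0 gives a difference of 12 h, SD 23.7, 80% power and two-sided 0.05. The normal approximation is n = 2(1.960 + 0.842)² × 23.7² / 12² = 61.2, or 62 per group. The exact t-test needs 62.2, rounded up to 63, with power 0.805. Allowing for 10% attrition, 63 / 0.90 = 70. The stated 63 and 70 reproduce, and nothing below changes them.

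**2. How finely each event is timed.**

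| Event | Where | Resolution |
|---|---|---|
| End of surgery | Appendix III, randomization sheet ("Surgery end time") | clock time |
| Discharge | Appendix III, day 3 sheet | day and time |
| Prunes | Appendix IV ("Mark on the chart below what time you ate a prune") | hourly grid |
| Docusate | Appendix V ("Mark on the chart below what time you took your stool softener medication") | hourly grid |
| First bowel movement | Appendix III, survey | date and time |
| Rescue laxative | Appendix III, survey, both languages | day only |

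Of the bowel agents the protocol provides, only the rescue laxative has no clock time. The diaries described in section 6.3 cover prunes, docusate and the first movement.

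**3. What can be ordered.** If the laxative day and the movement day differ, the order follows, provided the day can be matched to the calendar. The survey numbers docusate days 1 to 3 but asks for a date for the movement. If the two days are the same, the order is unknown from the forms.

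**4. How often they would be the same (illustration).** Assume doses are spread evenly over 08:00–22:00 and the movement follows L hours later. The two share a calendar day when the dose is before 24 − L, so the share is (16 − L)/14:
- L = 6: 10/14 = 71%
- L = 8: 8/14 = 57%
- L = 12: 4/14 = 29%

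**5. In numbers of women (illustration by simulation).** Planned inputs are 63 per arm, SD 23.7 and a 12 h difference. Assumed inputs are:
- normal times, with the means shown below;
- 30% of women still waiting take rescue, at a point spread over 48–96 h after surgery and between 08:00 and 22:00;
- surgery ends between 10:00 and 18:00;
- the movement comes 6 or 12 h after the dose, or sooner if it was due sooner.

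The last two columns give the number that certainly followed rescue (rescued minus same-day) up to the number rescued.

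| Arm mean (h) | Rescued | Same-day, 12 h lag | Same-day, 6 h lag | Reportable range, 12 h lag | Reportable range, 6 h lag |
|---|---|---|---|---|---|
| 60 | 6.5 | 2.5 | 4.6 | 4.0–6.5 | 1.9–6.5 |
| 72 | 9.6 | 3.5 | 6.8 | 6.1–9.6 | 2.8–9.6 |
| 84 | 12.7 | 4.4 | 8.9 | 8.3–12.7 | 3.8–12.7 |
| 96 | 15.3 | 5.0 | 10.8 | 10.3–15.3 | 4.5–15.3 |

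With a control mean of 84 h the prune mean is 84 − 12 = 72 h, so the two middle rows form one trial. At 15% uptake the 84 h row becomes 6.4 rescued, of whom 2.2–4.5 are same-day. At 50% it becomes 21.2 and 7.2–15.0.

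**6. What the planned analyses need.** The t-test needs only the time of the first movement. The chi-square test needs only whether a laxative was used. Neither uses the order.

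**The case against.** The strongest objection is that no planned analysis needs this information. That is correct, and it limits the point to what the report can describe.

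A second objection is that a laxative taken as needed was most plausibly taken before the first movement. In the simulation it always was, so the upper end of each range is the truth there. This is fair, and it makes the practical ambiguity smaller than the width of the ranges suggests. But the survey asks about any laxative use, not use before the first movement. A woman could also take one after a hard or painful first stool, and the forms would not show it.

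Third, hospital charts may hold times for doses given before discharge. That is possible, though the documents do not plan to use them and they would not cover doses at home. The loss is therefore mainly same-day pairs after discharge.

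A reader might go further and infer that rescue biases the prune comparison, or that the t-test is invalid. The documents do not support that. They do not say that rescue differs between arms, and similar timing in both arms causes no bias. Any dilution of the treatment difference would come from offering rescue at all, which a time field does not alter.

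**Conclusion.** The gap is real and small. It is certain from the forms that same-day doses and movements cannot be ordered. How many women this affects is not known, because the documents give neither rescue uptake nor timing. Under the assumptions above, with a 12 h lag and 30% uptake, the report at a control mean of 84 h could say only that 8 to 13 control movements followed rescue. With a 6 h lag, the widest case, it could say only 4 to 13. The counts scale with uptake and include in-hospital doses, some of which a chart might resolve.

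The primary t-test, the yes/no laxative endpoint and the sample size all stand. The change is worth considering because it costs almost nothing and has to be made before the forms are used.

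**What to change.** 1. On both language versions of the survey, replace the day question with: *When did you take the first laxative after surgery? Date ____ Time ____*

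2. Print on the sheet: *Please mail this sheet after day 3 and after your first bowel movement, whichever is later.* Sections 3.6 and 9.0 look for the sheet around postoperative day 3, while section 1.1 puts the mean time without intervention at 4 days, so late movements and doses could be missed. Both conditions are needed. If women mailed as soon as they had a movement, early movers would return the sheet before the day 1–3 docusate, prune and laxative items were complete, and probably more so in the prune arm. In the normal model, with a control mean of 84 h, 31% of controls and 50% of prune women move before 72 h.

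3. Add to section 13.0: *Every first bowel movement stays in the primary comparison, whether or not a laxative came before it. By arm, we will tabulate the number of first movements that followed a laxative and the hours from surgery end to first laxative dose.* Add no further test.

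The cost is one field and one printed line in two languages, and one descriptive table; there are no extra patients, visits or calls. Recalled times will be approximate. Sheets from slower women will arrive later, and a few may be forgotten. The table can show an imbalance in rescue but cannot correct for it.

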### 3.6 Evaluation Post-Intervention:

1. All participants will record the date and time of, consistency of and pain associated with their first bowel movement, and answer whether they experienced secondary outcomes as described later.

2. Participants in the treatment arm will also log the number of prunes consumed each day.

2. Participants will be given a stamped and addressed envelope to return the data collection sheets in. Participants will receive a call from an investigator masked to the treatment allocation on postoperative day 3 inquiring about whether the participant has mailed the data collection sheets back. Those who do not answer will be called again the next day.

3. During the phone call, if the participant indicates any postoperative concerns, she will be instructed to contact the on call physician at the LAC+USC Ob/Gyn Triage.

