## 7.2 Drug studies:

AGENT	DOSE	ROUTE	DAYS	NOTES
Prunes	4 oz/day	PO	3	Participant to eat any time during the day

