#### 9.0 CLINICAL AND LABORATORY EVALUATIONS AND STUDY CALENDAR

Parameter	Pre-Treatment	Postoperative day 1	Postoperative day 3*	Postoperative day 5*
Targeted history	X			
Operative history		X		
Postoperative Data Collection Sheet to be Mailed-In			X	X

\* If unable to reach patient by the telephone on postoperative day 3, another attempt will be made on postoperative day 5.

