#### 10.0 CRITERIA FOR EVALUATION AND ENDPOINT DEFINITIONS

The outcome status of all eligible patients will be reported. All eligible patients who begin treatment will be included in the analysis.

Primary endpoints: Time to first bowel movement (in hours)

Secondary endpoints:

1. Stool consistency of the first bowel movement as classified by the Bristol Stool Scale (The stool types are categorical variables, and we will evaluate the differences in the frequencies of the responses by treatment status with a chi-square test)
2. Pain with bowel movement measured (Likert scale, and assessed using t-test or non-parametric methods as appropriate)
3. Satisfaction with bowel regimen (Likert scale, and assessed using t-test or non-parametric methods as appropriate)
4. Satisfaction with surgery overall (Likert scale, and assessed using t-test or non-parametric methods as appropriate)
5. Requirements for laxative (yes or no, assessed as categorical variables and evaluated by chi-square test)
6. Compliance with docusate (percentage of medications consumed, and assessed using t-test or non-parametric methods as appropriate)
7. Compliance with prunes (percentage of prunes consumed, and assessed using t-test or non-parametric methods as appropriate)

8. Adverse events of extreme bloating or flatulence (yes or no, assessed as categorical variables and evaluated by chi-square test)

Compliance with prune consumption will be defined as reported successful consumption of 2/3 of the assigned prunes.

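### The postoperative day 3 call asks about mailing a sheet whose day-3 items are still open, so compliance and laxative use can be under-recorded

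*Combined protocol and SAP*

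**What the plan says.** **Intake period.** Section 3.5 states: "Participants in the treatment arm will receive a 12 oz package of prunes on the morning of postoperative day 1". The daily amount there is 12 prunes. Section 7.2 sets three days of prunes with the note "Participant to eat any time during the day". Section 6.3 gives docusate twice a day for three days. In Appendix IV the last row of each day's column is 5am the next morning.

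**What the sheet asks.** The self-administered survey in Appendix III asks for docusate and prune counts on each of three days, ending with "How many prunes did you eat on day 3". It also asks whether any laxative was used, which one and on what day. It gives no period for that question and has no field for the date or time of completion.

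**Return of the sheet.** Section 3.6 has a masked investigator telephone "on postoperative day 3 inquiring about whether the participant has mailed the data collection sheets back". In the section 9.0 calendar, the row "Postoperative Data Collection Sheet to be Mailed-In" is marked under postoperative days 3 and 5. For women not reached, section 3.6 says "Those who do not answer will be called again the next day", whereas the calendar footnote says "another attempt will be made on postoperative day 5".

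**Endpoints.** Section 10.0 lists laxative requirement (secondary endpoint 5), percentage of docusate taken (6) and percentage of prunes eaten (7). It adds: "Compliance with prune consumption will be defined as reported successful consumption of 2/3 of the assigned prunes".

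**The concern.** If day 1 on the sheet is postoperative day 1, day 3 is still running when the woman is asked whether her sheet is already in the post. If she has posted it, the sheet cannot cover the rest of that day. No section tells her to wait, and no later contact is described as collecting what is missing.

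Three secondary endpoints are exposed. Both compliance percentages can be recorded too low. The binary prune rule can misclassify women whose true intake is well above two thirds. Laxative use is counted up to whatever moment each woman posts. That moment can differ between women, and between arms if posting tends to follow the first bowel movement and prunes bring that event forward. Without a completion time, the analyst can neither see nor correct the difference.

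**Working it through.** **1. Dates.** Prunes are handed over on the morning of postoperative day 1 and last three days, so their third day is postoperative day 3. Section 6.3 describes three days of docusate directly after randomisation on the morning of postoperative day 1. That supports the same numbering for docusate without stating it. Appendix III does not define day 1.

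**2. Assigned amounts and the plan's threshold.**
- Prunes: 12 × 3 = 36. Two thirds of 36 is 24 (rule read as at least two thirds).
- Docusate: 2 × 3 = 6 intakes.

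**3. What a fully adherent woman can show.** Let f be the share of day 3 on the sheet when it is posted, with the rest counted as not taken. Recorded prune compliance is (24 + 12f)/36 and docusate compliance is (4 + 2f)/6.
- f = 0: 24/36 and 4/6, both 66.7%.
- f = 0.5: 30/36 and 5/6, both 83.3%.
- f = 1: 36/36 and 6/6, both 100%.

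The largest loss is therefore one third of the count, and there is none if day-3 intake was finished before posting.

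**4. The binary prune rule with day 3 absent and counted as zero.** Meeting 24 then requires all 24 prunes of days 1 and 2.
- 12 a day: 36/36 in truth, recorded 24/36. Still compliant.
- 11 a day: 33/36 (91.7%) in truth, recorded 22/36 (61.1%). Recorded as non-compliant.
- 8 a day: 24/36 in truth and compliant, recorded 16/36 (44.4%). Recorded as non-compliant.

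Reduced intake is foreseeable, because section 8.2 lets women cut down if they have side effects.

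**5. Effect on the mean.** If a share q of fully adherent women post with day 3 absent and it is counted as zero, mean recorded compliance is 1 − q/3. The documents give no value for q, so it is an assumption: 96.7% at q = 0.10, 91.7% at 0.25, 83.3% at 0.50 and 66.7% at 1.

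**6. Laxatives.** No rate of use is given, so under-recording cannot be sized. Whether the count could simply stop at the end of day 3 can be checked. Section 1.1 gives 4 ± 1.5 days to first bowel movement without intervention, that is, mean 96 h and SD 36 h. Section 13.0 uses an SD of 23.7, taken here as hours. If surgery ends between 6am and 6pm, a day-3 column closing at 6am on postoperative day 4 lies 84 to 96 h later. Under a normal approximation the share with no bowel movement by then is:
- at 84 h: 63.1% (SD 36 h) or 69.4% (SD 23.7 h);
- at 96 h: 50% with either SD.

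A cut-off there would exclude later laxative use while about half or more of the women might still be waiting.

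**7. Sample size.** The plan's 63 per group reproduces (t-test calculation 62.2, rounded up), and 63/0.9 = 70. Nothing in this point changes it.

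**The case against.** A reader might infer that sheets are due back by the postoperative day 3 call, so that every woman who posts on time under-reports. The documents do not support that. No deadline is stated, and asking whether the sheet has been mailed can serve as a reminder. The calendar also marks postoperative day 5, although its footnote ties that date to a repeat telephone attempt. The survey carries no day in its heading, the docusate diary in Appendix V runs to day 5, and the day-3 questions may themselves prompt a woman to finish the day before posting.

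Nor is a low count inevitable. A blank day-3 item is visible missing data and becomes zero only if someone scores it so, which no section instructs. This answer is incomplete, however: a woman who writes down her count so far leaves no blank, and without a completion time that entry looks final.

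The stakes are modest. Prune compliance concerns one arm only, so its error cannot bias a comparison between arms, and section 10.0 keeps all eligible women who begin treatment in the analysis whatever their compliance. Nothing in the documents links posting to the bowel movement, so unequal laxative windows between arms are a possibility and not a finding. The laxative question asks the day of use, which lets reported use be restricted to a common period, but it cannot recover use after posting. Section 3.5 says that laxative need will be recorded without limiting this to the sheet, yet it names no other source.

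What stands is the overlap itself, the missing posting instruction and the missing completion time.

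**Conclusion.** The concern holds as a gap in data collection: a sheet posted by the postoperative day 3 call can lack part or all of day 3, and the plan has no means of recovering it. This rests on day 1 being postoperative day 1, which sections 3.5 and 6.3 support.

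The loss is at most one third of the prune and docusate counts, and it applies only where missing intake is treated as not taken or a partial count is entered as final. Full adherence on days 1 and 2 still satisfies the prune rule; any shortfall on those days, with day 3 counted as zero, fails it. The frequency of early posting is unknown, so no overall bias can be stated. For laxatives, the defect is an undefined reporting period that ends at an unrecorded time; its size and direction cannot be derived from the documents.

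Secondary endpoints 5 to 7 are affected. The handling of women who have had no bowel movement when they post is a separate question about the primary endpoint. The change is worth making because it is cheap and because data missing from a posted sheet cannot be reconstructed under the plan.

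**What to change.** - In sections 3.6 and 9.0, move the first call to after day 3 has closed (postoperative day 4 or later), and reconcile the timing of the second call, which the two sections give differently.
- On the English and Spanish surveys, define day 1 as postoperative day 1, state that the sheet is to be posted only after the end of day 3, and add a completion date and time.
- In section 10.0 or 13.0, state that day-3 items left blank are missing, not zero.
- Compare laxative use over one stated window, the same in both arms, using the day-of-use item and not closing at the end of day 3. Because that window runs past the earliest permitted posting, say how use after posting is collected, or treat women whose sheet closes earlier as incompletely observed.

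**Cost.** One call already planned moves, and a few lines are added to each language version and to the analysis text. Treatment and sample size are unchanged. Sheets come back about a day or more later. Section 3.6 also uses this call to direct women with concerns to triage, so that contact would move as well, and the sponsor should confirm that this is acceptable.
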